15.2.2. Prior/Concomitant Medications/Procedures

Partially missing start/stop dates for prior/concomitant medications and partially missing start dates for prior/concomitant procedures will be imputed in the ADaM dataset for prior/concomitant medications/procedures. For prior/concomitant medications, if the stop date is complete with no missing year, month, or day, and the partially missing start date imputed by the rule below is after the stop date, then the start date will be imputed by the stop date.

Partially missing prior/concomitant medication/procedure start dates will be imputed by the earliest possible date given the non-missing field(s) of the date.

Partially missing prior/concomitant medication stop dates will be imputed by the latest possible date given the non-missing field(s) of the date.

15.2.3. Medical History

Partially missing medical history start dates will be imputed in the ADaM dataset for medical history (for the purposes of calculating durations of PsA and psoriasis). The 16th of the month will be used to impute a partially missing start date that has only the day missing, and July 1st will be used to impute a partially missing start date that has both the month and day missing.

15.2.4. Treatment Duration

Partially or completely missing last dose dates will be imputed in the ADaM dataset for treatment duration.

When partially missing last dose date is available, set last dose date to the maximum of [the earliest possible date given the non-missing field(s) of last dose date, the minimum of (the latest possible date given the non-missing field(s) of last dose date, last known date in database, first non-missing Early Termination (ET) visit date)]

When last dose date is completely missing, set last dose date to the minimum of (last known date in database, first non-missing Early Termination (ET) visit date)

Last known date in database is defined as maximum of the observed dates (i.e., last visit date, lab, vital signs, AE start or end dates, concomitant medications start or end dates, concomitant procedure date, last dose date from 'Disposition- Treatment' page, treatment exposure start or end dates where doses were completely or partially taken, death date).

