10. SAFETY ANALYSIS

Safety will be assessed via descriptive statistics and point estimates on observed data.

All safety analyses described in this section will be performed for both the Placebo-controlled Phase and the Apremilast Exposure Period. The safety analyses for the Placebo-controlled Phase will be based on the safety population and presented by treatment arm (placebo, and Apremilast 30 mg BID). The safety analyses for the Apremilast Exposure Period will be based on the Apremilast Exposure Population and presented by Apremilast dose group (i.e., Apremilast 30 mg BID) irrespective of the start time of Apremilast exposure (at Week 0 or 16). In addition, selected summaries on AEs for the Observational Follow-up Phase will be listed.

For the analyses of AEs and laboratory marked abnormalities, both subject incidence and exposure-adjusted incidence rate (EAIR) per 100 subject-years for the Placebo-controlled Phase (Weeks 0 to 16) and for the Apremilast Exposure Period will be provided. The point estimates of subject incidence and EAIR are distinguished as following:

- Subject incidence: is defined as the number of subjects with the specific event divided by the number of subjects included in the analysis (i.e., percentage [%] used in a frequency summary). Subjects with multiple occurrences of the specific event in the specific analysis period will be counted only once in the numerator.
- Exposure-adjusted incidence rate (EAIR) per 100 subject-years: The EAIR per 100 subject-years is defined as 100 times the number of subjects with the specific event divided by the total exposure time (in years) among subjects included in the analysis. Subjects with multiple occurrences of the specific event in the specific analysis period will be counted only once in the numerator. The exposure time for a subject without the specific event is the treatment duration (i.e., last dose date-first dose date+1), whereas the exposure time for a subject with the specific event is the treatment duration up to the start date (inclusive) of the first occurrence of the specific event. The total exposure time in years is calculated by dividing the sum of exposure time in days over all subjects included in the analysis by 365.25. The EAIR per 100 subject-years is interpreted as the expected number of subjects with at least one occurrence of the specific event per 100 subject-years of exposure to the IP.

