15.3. Tablets Intended to be Taken for Treatment Compliance Calculation

During the Placebo-controlled Phase (Weeks 0 to 16), blister cards with 33 rows of tablets (i.e., a maximum 33-day supply) will be supplied. A subject takes the first 5 rows of tablets (6 tablets per row/day) on each complete blister card before taking the remaining rows (2 tablets per row/day), and completes the first 28 rows, skips rows 29-33 (5-day extra supply) and starts a new blister card. It is also assumed that a subject takes the full day's tablets from a new blister card on a study drug dispense date.

Apremilast

Statistical Analysis Plan. Protocol CC-10004-PSOR-020

Amgen INC.

The intended total number of tablets is calculated as follows. First order the first dose date, the second dispense date, the third dispense date, etc., and the last dose date. The first and last dose dates are defined in the same way as those defined for treatment duration calculations.

The intended number of tablets between any 2 consecutive dates is calculated as

$$2 \times n + 4 \times \text{int}[(n + 27) / 28] + 4 \times \text{int}[(n + 26) / 28] + 4 \times \text{int}[(n + 25) / 28] + 4 \times \text{int}[(n + 24) / 28] + 4 \times \text{int}[(n + 23) / 28]$$

where n denotes the number of days between the 2 consecutive dates (ie, the second date minus the first date for all pairs of consecutive dates, and the second date minus the first date plus 1 for the last pair), and “int” denotes the integer part of the result. Then the intended total number of tablets is the sum of all intended numbers of tablets as calculated above from the first dose date through the last dose date.

During the Apremilast Extension Phase (Weeks 16 to 52), blister card with 33 rows of tablets will be supplied at Week 16 visit and open label bottles will be supplied at Week 20 through Week 52.

The intended number of tablets is calculated as follows. First order the first dose date, the second dispense date, the third dispense date, etc., and the last dose date. The first and last dose dates are for the treatments during the Apremilast Extension Phase. The intended number of tablets between any 2 consecutive dates is calculated as:

- $2 \times n + 4 \times \text{int}[(n + 27) / 28] + 4 \times \text{int}[(n + 26) / 28] + 4 \times \text{int}[(n + 25) / 28] + 4 \times \text{int}[(n + 24) / 28] + 4 \times \text{int}[(n + 23) / 28]$ for records on drugs in blister cards

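### SAP 15.2.4 lets a later off-treatment date replace a recorded last dose when the exposure-form date is completely missing and there is no ET visit, slightly overstating exposure

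*SAP*

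**What the plan says.** SAP 8.6 takes treatment duration from the first and last non-zero doses on the study drug exposure form, separately for each analysis phase or period.

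SAP 15.2.4 covers missing last dose dates. When the date is completely missing, the instruction is to "set last dose date to the minimum of (last known date in database, first non-missing Early Termination (ET) visit date"). It adds: "Last known date in database is defined as maximum of the observed dates". The list includes "last visit date, lab, vital signs, AE start or end dates, concomitant medications start or end dates", then procedure, exposure-record and death dates. The "last dose date from 'Disposition- Treatment' page" is one more entry in the same list.

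A partially missing date follows a separate rule, with an upper bound at "the latest possible date given the non-missing field(s) of last dose date".

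The resulting date is used in two further places:
- SAP 10, for the EAIR: "The exposure time for a subject without the specific event is the treatment duration (i.e., last dose date-first dose date+1").
- SAP 15.3, for the intended tablet count: "The first and last dose dates are defined in the same way as those defined for treatment duration calculations".

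**The concern.** When there is no ET visit date, only one term of the minimum is left, and that term is itself a maximum over mostly non-dosing dates. If the exposure form lacks the last dose but the Disposition page has it, the recorded dose survives only if nothing later is in the database.

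Later dates are expected by design. Protocol 10.1 records AEs until 28 days after the last dose. Protocol 10.2.6 follows unresolved serious events to recovery or death. SAP 5.2.4 summarizes concomitant medications up to 28 days post-treatment. SAP 5.2.4 and 5.5 also refer to the 4-week follow-up contact as a visit, so it may count as the last visit date.

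Days off drug would then be counted as exposure. That lengthens treatment duration, can move a subject into a longer exposure category, and enlarges the EAIR denominator.

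**Working it through.** The documents give no figure for this rule, so there is none to reproduce. The check has three parts.

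**1. What the rule returns**

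| Exposure-form last dose | ET visit | Result under 15.2.4 |
|---|---|---|
| Partially missing | Either | Bounded by the known month or year |
| Completely missing | Yes | No later than the ET visit |
| Completely missing | No | Latest date on the list, even if the Disposition page has an earlier last dose |

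Only the third row is a problem.

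**2. Effect on one affected subject**

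Duration = last dose date − first dose date + 1 (SAP 10). The shift is assumed to be 28 days, which is the protocol's AE collection window and follow-up interval.

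| True last dose | Imputed last dose | Overstatement |
|---|---|---|
| Day 35 | Day 63 | 28/35 = 80% |
| Day 40 | Day 68 | 28/40 = 70% |
| Day 56 | Day 84 | 28/56 = 50% |
| Day 84 | Day 112 | 28/84 = 33% |

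**3. Effect on pooled placebo-phase exposure**

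Inputs from SAP 4.4 and Table 4: 276 subjects, 24% discontinuing before Week 16, and a phase of 112 days. Assumptions: early leavers average 50 days on drug, and 5 to 20 subjects are affected, each by 28 days.

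- Completers: 276 × 0.76 × 112 = 23,493 days.
- Early leavers: 276 × 0.24 × 50 = 3,312 days.
- Total: 26,805 days, or 26,805/365.25 = 73.4 subject-years.
- 5 affected: 5 × 28 = 140 days, and 140/26,805 = 0.5%.
- 20 affected: 20 × 28 = 560 days, and 560/26,805 = 2.1%.

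For an event that few subjects have, the EAIR falls by almost the same proportion: 1 − 1/1.005 = 0.5% and 1 − 1/1.021 = 2.1%. An affected subject who has the event before the true last dose adds no excess, because person-time stops at onset.

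A simpler cross-check gives every subject 112 days and shifts a fraction f by 28 days, so rates are multiplied by 112/(112 + 28f). For f of 1%, 5% and 10%, rates fall by 0.25%, 1.2% and 2.4%.

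**The case against.** **Other sections supply limits.** SAP 8.6 computes duration by phase, SAP 5.2 gives each phase an end date, and SAP 10.1 stops the treatment-emergent window at the earlier of 28 days after last dose and the phase end. This stands in part. A reader might infer that nothing in the SAP bounds the imputed date, and that would be too strong. But 15.2.4 does not cite 5.2. For subjects lost to follow-up, 5.2 ends the phase on the last known study day, which is no stricter than the imputation rule.

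**The circumstances are narrow.** A subject who is truly lost has no follow-up contact, so the last known date will often be the last visit. A subject reached 4 weeks after stopping was contacted on a schedule counted from that stop, so the site knew roughly when dosing ended. This also stands, and it keeps the number affected low. It does not excuse the rule: where the stop date is known and entered on the Disposition page, 15.2.4 still lets a later date displace it.

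**Compliance.** A reader might infer that adherent early stoppers would be classed below 75%, because the later date raises the intended tablet count. For a last dose moved from Day 40 to Day 68, the 15.3 formula goes from 120 to 196 tablets, and 120/196 = 61%. That figure needs every unused tablet to have been returned.
- SAP 8.7 counts unreturned tablets as taken. Protocol Table 3 gives a subject who stops between Weeks 4 and 16 without an ET visit no scheduled return before Week 16.
- A card holds 5 × 6 + 28 × 2 = 86 tablets. Take 76 tablets from the first card. One unreturned later card gives (76 + 86)/196 = 83%. Three, assumed dispensed at Week 4 to cover 12 weeks, give (76 + 258)/196 = 170%.
- With only a Week 0 dispense record, SAP 8.7 calculates no compliance.

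The direction of the compliance error therefore depends on tablet return, and the documents do not support a claim that compliance is understated.

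**Conclusion.** The point holds for completely missing exposure-form last dose dates with no ET visit. As written, 15.2.4 can replace a recorded last dose with a later off-treatment date. This is a fault in the rule itself, beyond any missing detail. It overstates treatment duration and EAIR person-time for those subjects, and so slightly understates EAIRs.

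The effect is large for an affected subject and small overall. The 0.5% to 2.1% range for placebo-phase exposure rests on the assumed 5 to 20 subjects, the full 28-day shift and the 50-day average for early leavers, none of which the documents give.

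A reader might also infer that the treatment comparison of safety rates is biased. That would require the missing dates to differ between arms, and nothing in the documents shows that they would. The primary efficacy analysis does not use this date. This is a low-priority correction.

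**What to change.** Amend SAP 15.2.4 for completely missing dates:

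1. Use the Disposition-page last dose date whenever it is present.
2. Otherwise use the earliest of the ET visit date, the end of the analysis phase as defined in 5.2, and the latest on-treatment date (last dosing record or last scheduled treatment-phase visit).
3. Remove follow-up contact, AE end, concomitant medication, procedure and death dates from the maximum.

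The cost is a few lines of SAP text and a small programming change, with no new data. The downside is that exposure may be slightly understated for a lost subject who went on taking tablets after the last visit. If a phase-end cap is already intended, writing it into 15.2.4 removes the ambiguity.

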15.3. Tablets Intended to be Taken for Treatment Compliance Calculation

During the Placebo-controlled Phase (Weeks 0 to 16), blister cards with 33 rows of tablets (i.e., a maximum 33-day supply) will be supplied. A subject takes the first 5 rows of tablets (6 tablets per row/day) on each complete blister card before taking the remaining rows (2 tablets per row/day), and completes the first 28 rows, skips rows 29-33 (5-day extra supply) and starts a new blister card. It is also assumed that a subject takes the full day's tablets from a new blister card on a study drug dispense date.

Apremilast

Statistical Analysis Plan. Protocol CC-10004-PSOR-020

Amgen INC.

The intended total number of tablets is calculated as follows. First order the first dose date, the second dispense date, the third dispense date, etc., and the last dose date. The first and last dose dates are defined in the same way as those defined for treatment duration calculations.

The intended number of tablets between any 2 consecutive dates is calculated as

$$2 \times n + 4 \times \text{int}[(n + 27) / 28] + 4 \times \text{int}[(n + 26) / 28] + 4 \times \text{int}[(n + 25) / 28] + 4 \times \text{int}[(n + 24) / 28] + 4 \times \text{int}[(n + 23) / 28]$$

where n denotes the number of days between the 2 consecutive dates (ie, the second date minus the first date for all pairs of consecutive dates, and the second date minus the first date plus 1 for the last pair), and “int” denotes the integer part of the result. Then the intended total number of tablets is the sum of all intended numbers of tablets as calculated above from the first dose date through the last dose date.

During the Apremilast Extension Phase (Weeks 16 to 52), blister card with 33 rows of tablets will be supplied at Week 16 visit and open label bottles will be supplied at Week 20 through Week 52.

The intended number of tablets is calculated as follows. First order the first dose date, the second dispense date, the third dispense date, etc., and the last dose date. The first and last dose dates are for the treatments during the Apremilast Extension Phase. The intended number of tablets between any 2 consecutive dates is calculated as:

- $2 \times n + 4 \times \text{int}[(n + 27) / 28] + 4 \times \text{int}[(n + 26) / 28] + 4 \times \text{int}[(n + 25) / 28] + 4 \times \text{int}[(n + 24) / 28] + 4 \times \text{int}[(n + 23) / 28]$ for records on drugs in blister cards
- $2 \times n$ for records on drugs in open label bottles.

Then the intended total number of tablets is the sum of all intended numbers of tablets as calculated above from the first dose date through the last dose date.

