Abbreviations: BMI = body mass index; BSA = body surface area; [REDACTED] DLQI = Dermatology Life Quality Index; EQ-5D = European Quality of Life 5-Dimension; FCBP = females of childbearing potential; IP = investigational product; NAPSI = Nail Psoriasis Severity Index; PASI = Psoriasis Area Severity Index; PBQ = Patient Benefit Questionnaire; PNQ = Patient Needs Questionnaire; PPPGA = Palmoplantar Psoriasis Physicians Global Assessment; NRS = Numeric Rating Scale; ScPGA = Scalp Physician Global Assessment; sPGA = static Physicians Global Assessment; sPGA-G = static Physicians Global Assessment of Genitalia; VAS = Visual Analog Scale; WPAI:PSO = Work Productivity and Activity Impairment Questionnaire: Psoriasis.

^a Visits in the Placebo-controlled Phase to be performed ± 3 days.

^b Visits in the Apremilast Extension Phase to be performed ± 4 days.

^c Visit 9 will serve as the Early Termination Visit for any subject who prematurely discontinues from the study, prior to Week 52. All subjects who complete the study or discontinue the study early will be asked to enter the Four-week Post-treatment Observational Follow-up Phase.

^d Post-treatment observational follow-up will be conducted by telephone.

^e Written informed consent will be obtained by the Principal Investigator or designee prior to initiation of any study procedures, including washouts from prior medications.

^f Adverse event review should include new or worsening psychiatric symptoms, suicidal ideation, suicidal attempt, severe diarrhea, nausea and vomiting, and unexplained and clinically significant weight loss. See Section 6.5.

^g Females of childbearing potential (FCBPs) only. Serum pregnancy tests are performed at Screening, and Early Termination Visit/Last Treatment Visit. Urine pregnancy test kit will also be provided to the site and performed at baseline prior to randomization. The Investigator will educate all FCBP about the different options of contraceptive methods and their correct use at Screening and Baseline visits. The subject will be reeducated every time their contraceptive measures/methods or their ability to become pregnant changes. A pregnancy test(s) should be administered if the FCBP subject misses a menstrual period.

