6.2. Treatment Period

The subject will begin treatment upon confirmation of eligibility. The subject must start treatment within 35 days (5 weeks) of signing the ICF. An administrative window of ± 3 day is permitted for Visits 3 and 4 and ± 4 days is permitted for Visits 5 through 9.

The following procedures will be conducted as outlined in the Table of Events, [Table 3](#). The evaluations should be performed prior to dosing on the visit day, unless otherwise specified.

- Inclusion/Exclusion criteria (Baseline/Visit 2)
- Concomitant medications and therapies evaluation
- Vital signs
- Weight, waist circumference
- Adverse event evaluation (continuously and through 28 days after last dose of apremilast)
- Clinical laboratory evaluations [If screening laboratory assessments are within 7 days of Baseline (Week 0), laboratory assessment does not need to be repeated at Baseline (Week 0)]
- Efficacy assessment (see Section [6.4](#)) [In addition to assessments specified in [Table 3](#), investigator will follow country guidelines to monitor therapy outcomes according to clinical routine care and may assess efficacy or safety at any unscheduled visit and document in source documents.]
- Dispense IP
- Return and count IP tablets
- Urine (or serum) pregnancy test (prior to dosing on Day 1)

Approved

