7.4. Packaging and Labeling

The label(s) for IP will include Sponsor name, address and telephone number, the protocol number, IP name, dosage form and strength (where applicable), amount of IP per container, lot number, expiry date (where applicable), medication identification/kit number, dosing instructions, storage conditions, and required caution statements and/or regulatory statements as applicable. Additional information may be included on the label as applicable per local regulations.

All IP tablets, including apremilast and identically-appearing placebo, will be supplied by Amgen. Investigational product for dose titration at Baseline and to Week 20 will be supplied in blister cards. Investigational product tablets at Week 20 and through Week 52 will be supplied in open label HDPE bottles with child-resistant caps.

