Appendix R: Titration Blister Card

30mg BID Titration and Treatment Card (28 day +5 Extra)

	1	10	20p	30p	1	10p	20p	30p
	2	10	20p	30p	2	10p	20p	30p
	3	10	20p	30p	3	10p	20	30p
	4	10p	20	30p	4	10p	20	30p
	5	10p	20	30p	5	10p	20p	30
	6		30		6		30	
	7		30		7		30	
	8		30		8		30	
	9		30		9		30	
	10		30		10		30	
	11		30		11		30	
	12		30		12		30	
	13		30		13		30	
	14		30		14		30	
	15		30		15		30	
	16		30		16		30	
	17		30		17		30	
	18		30		18		30	
	19		30		19		30	
	20		30		20		30	
	21		30		21		30	
	22		30		22		30	
	23		30		23		30	
	24		30		24		30	
	25		30		25		30	
	26		30		26		30	
	27		30		27		30	
	28		30		28		30	
	29		30		29		30	
	30		30		30		30	
	31		30		31		30	
	32		30		32		30	
	33		30		33		30	

Approved

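### SAP 15.3 restarts 6-tablet days on day 29 for a Week 16 supply that reads as one card, so intended tablets are overcounted when the Week 16-20 interval is 29 days or more

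*SAP*

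**What the plan says.** SAP 8.7 defines compliance as tablets taken divided by tablets that should have been taken in the phase. It reports the categories below 75%, 75% to 120%, and above 120%. Protocol 9.9.1 uses the same 75-120% band. SAP 15.3 supplies the denominator.

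For the Placebo-controlled Phase, SAP 15.3 assumes 6 tablets a day from the first five rows of each 33-row card and 2 a day from the later rows. The subject then "completes the first 28 rows, skips rows 29-33 (5-day extra supply) and starts a new blister card". The formula repeats every 28 days to match.

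For the Extension Phase, SAP 15.3 says "blister card with 33 rows of tablets will be supplied at Week 16 visit and open label bottles will be supplied at Week 20". It nevertheless prescribes the same 28-day formula "for records on drugs in blister cards", and 2 tablets a day for bottles.

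Protocol Appendix R titles the card "30mg BID Titration and Treatment Card (28 day +5 Extra" and shows 33 rows. Protocol 7.4 says: "Investigational product for dose titration at Baseline and to Week 20 will be supplied in blister cards". On timing, the Table 3 footnotes say "Visits in the Placebo-controlled Phase to be performed ± 3 days" (this covers Week 16) and "Visits in the Apremilast Extension Phase to be performed ± 4 days" (this covers Week 20). Protocol 6.2 differs for Week 16: "4 days is permitted for Visits 5 through 9".

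**The concern.** The restart on day 29 makes sense only if a fresh card is opened that day. The Week 16 supply reads as a single card that lasts until bottles arrive at Week 20. On that reading, a subject who comes late to Week 20 moves on to rows 29-33, which hold 2 tablets each. The formula instead charges 6 tablets for each of those days.

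The error runs one way: it inflates the denominator and lowers reported compliance. From day 30 the intended count exceeds all the tablets on the card. At stake is whether some subjects are placed in the below-75% category in the extension compliance table when they took well over 75% of what was due.

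**Working it through.** **Inputs.** Rows 1-5 hold 6 tablets and rows 6-33 hold 2 (SAP 15.3, Protocol Appendix R). One card therefore holds 5×6 + 28×2 = 86 tablets, and its first 28 rows hold 5×6 + 23×2 = 76. For a subject who continues, n is the Week 20 dispense date minus the first extension dose date. For a subject who stops before Week 20, n runs to the last dose date, plus 1 (SAP 15.3).

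**SAP formula.** f(n) = 2n + 4 × Σ int[(n+k)/28], k = 23 to 27. Counting tablets day by day under the new-card-every-28-days rule gives the same value for every n from 1 to 140. The formula is therefore a correct rendering of the Placebo-controlled Phase rule.

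**One card, no restart.** Tablets due are 2n + 4 × min(n, 5), which is 2n + 20 for n of 5 or more.

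| n (days) | SAP formula | 2n + 20 | Excess | Score if all due tablets taken, last dose on day n |
|---|---|---|---|---|
| 28 | 76 | 76 | 0 | 100% |
| 29 | 82 | 78 | 4 | 78/82 = 95.1% |
| 30 | 88 | 80 | 8 | 80/88 = 90.9% |
| 31 | 94 | 82 | 12 | 82/94 = 87.2% |
| 32 | 100 | 84 | 16 | 84/100 = 84.0% |
| 33 | 106 | 86 | 20 | 86/106 = 81.1% |
| 34 | 108 | 88 | 20 | card finished on day 33 |
| 35 | 110 | 90 | 20 | card finished on day 33 |
| 36 | 112 | 92 | 20 | card finished on day 33 |

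**Can such intervals occur?** With Table 3 offsets a from -3 to 3 at Week 16 and b from -4 to 4 at Week 20, the interval is 28 + b - a, with a maximum of 28 + 4 + 3 = 35. Of the 7×9 = 63 offset pairs, 28 give 29 days or more and 21 give 30 or more. This counts combinations and does not forecast frequency. With ±4 at both visits (Protocol 6.2) the maximum is 36.

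**Extension completers.** Take 36 weeks = 252 days, with the remaining days at 2 tablets from bottles and every available tablet taken.

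- n = 32: (84 + 440)/(100 + 440) = 524/540 = 97.0%.
- n = 35: (86 + 434)/(110 + 434) = 520/544 = 95.6%.
- n = 36: (86 + 432)/(112 + 432) = 518/544 = 95.2%.

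Without the restart, the denominator is 2×252 + 20 = 524 at each of these intervals. The scores become 100%, 520/524 = 99.2% and 518/524 = 98.9%. The small remaining shortfall at 35 and 36 days is the 2 or 3 days after the card runs out.

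**Partly adherent subjects who stop.** With the last dose on day 32 and 74 of 84 tablets taken, true compliance is 74/84 = 88.1%. The score is 74/100 = 74.0%, in the below-75% category. On day 33, 79 of 86 is 91.9% and is scored 79/106 = 74.5%.

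**The case against.** The strongest objection is that the documents never print the number of cards dispensed at Week 16. The single card rests on the singular wording in SAP 15.3, the 28 + 5 day layout and the change to bottles at Week 20. Protocol 7.2 and 7.4 use the plural, which may simply refer to subjects collectively and does not settle the matter. If two cards are supplied, the formula follows the SAP's own rule and the overcount disappears. This stands, so the point is conditional.

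Three stronger readings are tempting, and the documents do not support them.

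- A reader might put 86 over 110 and infer a full-adherence score of 78.2% at 35 days. For a subject who stops, n ends at the last dose, and a fully adherent subject finishes one card on day 33. The lowest such score is 81.1%. A lower one would need a missing last dose date imputed to a later day under SAP 15.2.4.
- A reader might cap the tablets due at 86. SAP 8.7 asks what should have been taken, and dosing is twice daily throughout. The cap would measure supply, and it would credit full compliance to days without drug.
- A reader might extend the point to Weeks 0-4. For that phase SAP 15.3 expressly has the subject start a new card after row 28, so without a card count no error is shown there.

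It is also fair that the effect is small. The formula is exact at the scheduled 28 days, and both arms use the same tablet layout at Week 16 (Protocol Appendix Q).

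**Conclusion.** On the natural single-card reading, SAP 15.3 gives a wrong denominator for Week 16-20 intervals of 29 days or more, and such intervals are within the permitted windows. The excess is 4 tablets at day 29, rises by 4 a day to 20 at day 33, and stays at 20.

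Subjects who take every tablet due remain inside the 75-120% band. The subjects at risk are partly adherent ones whose last dose falls after day 28 but before any bottle is dispensed; they can be scored below 75% when true compliance is near 90%. How many there will be cannot be judged from the documents.

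A reader might infer that the efficacy results or the per-protocol set are affected. They are not: no efficacy analysis uses the compliance rate, and the per-protocol definition in SAP 5.3.2 concerns deviations affecting the Placebo-controlled Phase. The consequence is confined to a descriptive table, so the correction is optional but worthwhile. Confidence is medium because the card count is unstated.

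**What to change.** State in SAP 15.3 how many cards are dispensed at each visit. If one is dispensed at Week 16, use 2n + 4 × min(n, 5) for that blister record, with no restart on day 29 and no 86-tablet cap. Keep 2n for bottles.

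As a general rule, limit the 6-tablet days to five per card actually dispensed. This leaves the restarts in place wherever further cards are supplied. It also prevents one more restart than there are cards if the Weeks 4-16 interval runs long.

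The cost is one line in the SAP and in the program. No new data are needed beyond the dispensing records, and only descriptive compliance figures change.
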